3.5 Inclusion Criteria

Each subject must meet the following criteria to be enrolled in this study.

- 6. A clinical diagnosis of CD for at least 3 months prior to screening corroborated by prior endoscopic and histopathologic documentation consistent with CD.
- 7. Quiescent to mildly active inflammatory CD defined with a total SES-CD score of < 10 or FCP < 500 mcg/g within 4 weeks before Screening
- Moderate to severe abdominal pain as defined by average abdominal pain score (AAPS) of ≥4 points on 7 consecutive days of the screening period up to Day -2. AAPS will be based on the 11-point numeric rating scale where 0 (no abdominal pain) to 10 (worst possible abdominal pain)

[figure not shown]

[figure not shown]

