Dosage:	APD371 dosed at 25 mg or 100 mg three times daily (TID) at approximately $07:00 \pm 2$ hr, $15:00 \pm 2$ hr and $23:00 \pm 2$ hr for 8 weeks (Wk).
Concurrent Control:	Intra-subject screening (baseline)

[figure not shown]
Route and Formulation:	Oral, capsules which are identical for each dose
Objectives:	 Key Objective To assess the tolerability and safety of two doses of APD371 in subjects with Crohn's Disease (CD) experiencing abdominal pain treated for up to 8 Wk.
	 Exploratory Objectives: Determination of pharmacokinetic (PK) profiles (including metabolites) and average PK parameters (C_{max}, t_{max}, AUC₀₋₈) of two doses of APD371 TID Change in abdominal pain score (APS) from pre-dose (trough) to 1.5 hr post-dose (peak) following the first of 3 daily doses of APD371; assessed daily to Day 56 and averaged weekly to Wk 8
	 Change in average abdominal pain score (AAPS) from baseline to Wk 8 (averaged weekly to Wk 8) Proportion of subjects who are weekly responders Proportion of subjects who are end-of-treatment responders Number of pain-free days per week, based on responses to the Abdominal Pain Severity Pain medication use Effect of APD371 treatment on reduction in C-reactive protein (CRP) and other biomarkers at week 4 and week 8
Study Design:	 Effect of APD371 treatment on reduction in fecal calprotectin at week 4 and week 8
Sudy Design:	A randomized, open label, parallel group, multi center, comparison of two doses of APD371.Eligible subjects will enter a screening period of up to 4 weeks and will then be randomized in a 1:1 ratio to receive APD371 in doses of 25 mg or 100 mg TID for 8 weeks.

	Randomization will be stratified by sex.

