5.2 Medical History

During the Screening Visit, a complete medical history and a social history, including smoking, caffeine, and alcohol use, will be collected by subject interviewer. Concomitant medications, recent blood donations, illnesses, and participation in other investigational drug studies will also be recorded. A review of the subjects screening medical history will be performed at the time of presentation on Day 1 (pre-treatment) to update findings including the requirement for a AAPS \geq 4 (from a subject diary) and to document any pre-treatment AEs.

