5.5 Abdominal Pain assessment

5.5.1 Abdominal Pain Score and Average Abdominal Pain Score

The abdominal pain score (APS) is a PRO using an NCR rating scale which is recorded in a subject diary. The 11 point NCR scale ranges from 0 [no abdominal pain] to 10 [worst possible abdominal pain] will be recorded by subjects in a diary as follows;

During Screening. Twice daily for at least 7 consecutive days within the initial Screening period (Day -28 to Day-1), at the following times;

- 1. Early morning, approximately 06:00 08:00
- 2. Late evening, approximately 20:00 22:00.

The Screening assessment of AAPS will be based on the average of the last (most recent) 7 days of morning and evening diary records within the screening period.

During Treatment. Three times a day on each treatment Day (Day 1 to 56) at the following times;

- 1. Before the morning dose and before any other morning dose study procedures
- 2. Approximately at 1.5 hours after the morning dose
- 3. Before the evening dose.

Note: Subjects will also be required to complete the diary before their first morning dose on Wk 0 (Day 1), and at the End-of-Treatment Visit at Wk 8 in the early morning (06:00 - 08:00). If a subject discontinues the study, Early Termination, the APS score will be assessed.

The average abdominal pain Score (AAPS) is the average of the APS score over each weekly assessment period (Wk 1 to Wk 8). These average scores will be determined automatically in the eCRF from the diary cards records inserted into the eCRF.

If a subject changes dose during the course of the study, they will maintain their daily APS scoring.

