3.3.2. Exploratory Endpoints

3.3.2.1. Abdominal Pain Score (APS) and Average Abdominal Pain Score (AAPS)

The APS is a PRO using a numerical rating scale (NRS) which is recorded in a subject diary. The 11-point NRS scale ranges from 0 (no abdominal pain) to 10 (worst possible abdominal pain) will be recorded by subjects in a diary as follows;

During Screening Period

APS is recorded twice daily for at least 7 consecutive days within the Screening period (Day -28 to Day -1), at the following times:

- 1. Early morning, approximately 06:00 08:00
- 2. Late evening, approximately 20:00 22:00

To establish a baseline for AAPS the following procedure will be adopted:

The last diary entry prior to treatment will be identified. The 7 consecutive days that terminate with this last data point constitute the Screening reference period. Baseline for AAPS is the mean of non-missing pain scores within the Screening reference period.

During Treatment Period

APS is recorded three times a day on each treatment Day (Day 1 to 56) at the following times:

- 1. Before the morning dose and before any other morning dose study procedures (i.e., at trough APD371 concentration)
- 2. Approximately 1.5 hours after the morning dose (i.e., at peak APD371 concentration)
- 3. Before the evening dose (i.e., at evening trough ADP371 concentration)

Note: Subjects will also be required to complete the diary before their first morning dose on Wk 0 (Day 1), and at the EOT Visit at Wk 8 in the early morning (06:00 - 08:00). If a subject discontinues the study, ET, the APS score will be assessed.

It should be noted that:

- The AAPS is derived for each assessment period (Wks 1, 2, 4, 6, 8). For Wks 4, 6, and 8 scores are collected from the previous 7 days of diary entries prior to the visit day. 'Peak AAPS' is the mean of non-missing APS recorded at the time of peak concentration for those 7 days. Likewise, 'Trough APS' is the mean of non-missing APS recorded at the time of trough concentration for those 7 days. Similarly, 'Evening Trough APS' is the mean of non-missing APS recorded at the time of evening trough concentration for those 7 days. Wk 1 and Wk 2 peak, trough, evening trough, and overall AAPS are derived in a similar manner but note that:
 - For Wk 1, as Day 1 is neither peak nor trough, and APS scores cannot be accurately identified as pre-dose or post-dose, scores on Day 1 are disregarded. Hence, AAPS scores may be obtained from fewer than 7 days.

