5.3. Protocol Violations

Significant protocol violations will be tabulated displaying frequencies and percentages of the Efficacy population falling into the following categories:

- Treated despite violating inclusion criterion 8 (i.e., screening AAPS of \geq 4)
- Treated with dose other than the dose the subject was randomized to receive
- Developed withdrawal criterion but was not discontinued from treatment
- Less than 80% compliance

6. **DEMOGRAPHICS AND BASELINE CHARACTERISTICS**

6.1. **Demographics**

Demographic and baseline characteristics data (age, height, weight, BMI), social history (smoking, caffeine, alcohol use), medical history (abnormalities only), physical examination (abnormalities only), and concomitant medications at study entry will be listed for all subjects. Demographic and Baseline Characteristics of the Safety and Efficacy populations will be summarized by treatment group and for the overall population.

Baseline for the demographic and baseline characteristic variables will be the last prerandomization value. Continuous variables will be summarized using number of observations (n), mean, SD, median, minimum, and maximum. Frequencies and percentages will be reported for all categorical data. No formal statistical testing comparing treatment groups will be performed.

The following variables will be summarized by treatment group and overall:

Continuous demographic and Baseline characteristic variables: age (years), height (cm), weight (kg), body mass index (BMI; kg/m²), and simple endoscopic score Crohn's disease (SES-CD).

Categorical demographic and Baseline characteristic variables: sex (female or male), ethnicity (Hispanic/Latino or Not Hispanic/Not Latino) and race (American Indian or Alaska Native; Asian; Black or African American; Native Hawaiian or Other Pacific Islander; White; Other, specify) nicotine consumption (never, former, current), and alcohol consumption (never, former, current).

Baseline SES-CD, an optional assessment by colonoscopy, will be presented in subject listing.

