8.2. Average Abdominal Pain Score (AAPS)

AAPS is the average of the APS score over each weekly assessment period (Wks 1, 2, 4, 6, 8). The Baseline value of AAPS will be derived as the average of the last (most recent) non-missing 7 days of morning and evening diary records within the Screening period prior to Day 1 of treatment. During the treatment period, summaries for a nominal week will be derived from the last 7 days within that period that contain a non-missing assessment. Summaries may be derived from fewer than 7 days (e.g., if the Wk 1 and Wk 2 Visits are less than 7 days apart). AAPS will be summarized for the Screening period and for each assessment week of treatment before morning dose (trough) assessments and 1.5 hours post-treatment first daily dose (peak) assessments, by treatment group and overall. Statistical comparisons of AAPS will be made between Screening and Wk 4 and Wk 8, trough and peak assessments, by treatment and overall. Change scores from Baseline for peak and trough at Wk 4 and Wk 8 will be derived. Treatment comparisons of the change scores will be analyzed using ANCOVA as for AAPS. The adjusted

treatment effect, 95% CI, and p-value will be presented. Overall changes from Baseline at Wk 4 and Wk 8 will be assessed using 1-sample t-tests as for AAPS. These analyses will be repeated for the Per Protocol population.

Peak and trough AAPS by treatment and visit will be plotted displaying treatment means and 95% CIs for the efficacy population only.

These analyses will be repeated where AAPS will be summarized for the Screening period and for each assessment week of treatment before evening dose (evening trough) assessments and 1.5 hours post first daily dose (peak) assessments, by treatment group and overall.

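### The screening week that qualifies a subject on AAPS ≥4 is almost the same week that serves as Baseline AAPS, so with no placebo arm the change from Baseline and the responder rates are biased towards benefit by regression to the mean

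*Protocol*

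**What the plan says.** **Entry.** Protocol 3.5, criterion 8, requires an "average abdominal pain score (AAPS) of ≥4 points on 7 consecutive days of the screening period up to Day -2". Protocol 5.5.1 adds: "The Screening assessment of AAPS will be based on the average of the last (most recent) 7 days of morning and evening diary records". On Day 1, before treatment, Protocol 5.2 has the site "update findings including the requirement for a AAPS" of at least 4, read from the diary.

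**Baseline.** SAP 3.3.2.1 finds the last diary entry before treatment and states: "The 7 consecutive days that terminate with this last data point constitute the Screening reference period". It continues: "Baseline for AAPS is the mean of non-missing pain scores within the Screening reference period". SAP 8.2 restricts the records to morning and evening entries made in screening before Day 1.

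**Control.** The Protocol synopsis gives the concurrent control as "Intra-subject screening (baseline"). Subjects are randomised 1:1 to 25 mg or 100 mg TID, open label. There is no placebo or untreated arm.

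**Use.** SAP 8.2 says that overall changes from Baseline at Wk 4 "and Wk 8 will be assessed using 1-sample t-tests as for AAPS". SAP 3.3.2.2 defines every responder by a reduction of at least 30% from the same Baseline. SAP 5.3 counts as a significant violation any subject "Treated despite violating inclusion criterion 8", which it explains as the screening AAPS requirement.

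Neither document mentions regression to the mean, a run-in, or a Baseline kept apart from the qualifying week.

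**The concern.** A weekly pain average is the subject's usual level plus that week's fluctuation. Admitting only subjects whose average reaches 4 favours those whose fluctuation was upward that week. If the same week is then the reference, later weeks are expected to be lower even on an inert drug. A concurrent placebo arm would show the same fall and allow it to be subtracted; this trial has none.

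Protocol 8.2 expects the trial to quantify the extent of pain relief. The outputs that would be read that way are the pooled and within-arm change from Baseline and the absolute responder proportions, and these carry the bias.

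There is also a documentary problem. The passages defining the qualifying and Baseline weeks do not give the same end day, so a subject correctly admitted can have a Baseline below 4.

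**Working it through.** **Inputs from the documents.** Threshold 4 on a 0 to 10 scale (Protocol 3.5); about 16 subjects (Protocol 3.1); 1-sample t-tests on change (SAP 8.2); responder cut-off 30% (SAP 3.3.2.2); nominal two-sided p-values and 95% intervals (Protocol 8.1). The plan states no effect size, SD, correlation or power, so there is no figure to reproduce.

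**Inputs assumed.** Candidates' mean pain, SDs and correlations, given as ranges below.

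**1. Closed form for an inert drug.** Let SD be the spread of weekly AAPS among candidates and ρ the correlation between the screening week and a treatment week.

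Expected fall = SD × (1 − ρ) × φ(a) / (1 − Φ(a)), with a = (4 − mean) / SD.

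- Mean 4, SD 2.0, ρ 0.7: a = 0; 2.0 × 0.3 × (0.399 / 0.5) = 0.48 points.
- Mean 5, SD 1.5, ρ 0.8: a = −0.667; 1.5 × 0.2 × (0.319 / 0.748) = 0.13 points.
- Mean 6, SD 1.5, ρ 0.9: a = −1.333; 1.5 × 0.1 × (0.164 / 0.909) = 0.03 points.

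For SD 1.5 to 2.0 and ρ 0.5 to 0.9, the fall is 0.12 to 0.80 at mean 4, 0.06 to 0.51 at mean 5 and 0.03 to 0.29 at mean 6.

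**2. Daily diary simulation, inert drug, n = 16.** Daily score = subject mean + AR(1) deviation, limited to 0 to 10. Between-subject and day-to-day SDs are 1.5 to 2 and the AR(1) coefficient is 0.5 to 0.8. The Wk 8 week keeps the subject's mean and draws a fresh deviation.

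| | Baseline = qualifying week, candidate mean 4 to 5 | Baseline = qualifying week, candidate mean 6 | Baseline = following week, candidate mean 4 to 5 |
|---|---|---|---|
| Expected fall (points) | 0.2 to 0.9 | 0.1 to 0.4 | 0.02 to 0.37 |
| Nominal two-sided rejection | 9% to 41% | 6% to 11% | 5% to 10% |
| False ≥30% responders | 8% to 34% | 6% to 20% | 6% to 28% |

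**3. Does ending the qualifying week at Day -2 help?** Hardly. With between-subject SD 1.4, day-to-day SD 1.8 and AR(1) 0.7, the fall at mean 4 is 0.70 when the two weeks are identical and 0.67 when the qualifying week is Day -8 to -2 and Baseline is Day -7 to -1. At mean 5 it is 0.43 against 0.42. Six of the seven days are shared.

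**4. How much does a separate Baseline week remove?** At the large end the fall goes from 0.92 to 0.37, a cut of 1 − 0.37/0.92 = 60%. At the small end it goes from 0.19 to 0.02, a cut of 1 − 0.02/0.19 = 89%. If the qualifying week is moved back to Day -28 to -22, the residual fall is 0.00 to 0.05. Responders persist: in the mean 4 case of step 3 they go from 28% only to 19%, because ordinary week-to-week variation alone yields 30% drops.

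**5. The windows side by side.**

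| Place | Window for the 7 days |
|---|---|
| Protocol 3.5, criterion 8 | Within screening, up to Day -2 |
| Protocol 5.5.1 | Most recent 7 days of screening (Day -28 to Day -1) |
| SAP 3.3.2.1 | 7 days ending at the last entry before treatment |
| SAP 8.2 | Most recent 7 non-missing days of screening, before Day 1 |

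Taking Day -8 to -2 for entry and Day -7 to -1 for Baseline, about 2.5% to 6.6% of correctly admitted subjects have a Baseline below 4 under the step 2 assumptions at candidate mean 4 to 5. In 16 subjects that is 16 × 0.025 = 0.4 to 16 × 0.066 = 1.1. If Protocol 5.2 is read as re-applying the threshold to the latest week, such subjects would be stopped on Day 1, but Baseline would then be fully selected on being high.

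**The case against.** **The randomised comparison is sound.** A reader might infer that all the pain results are compromised, or that the screening value is the trial's only comparator. The documents do not support that. The 25 mg and 100 mg arms regress equally in expectation and are compared by ANCOVA with Baseline as covariate. The peak-minus-trough contrast in SAP 8.1 takes both terms from the treatment period. Neither is biased this way. This stands and limits the point to pooled and within-arm change from Baseline and absolute responder rates. The ANCOVA does not repair those.

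**The fall is not guaranteed.** It is an expectation, and 16 subjects may not show it. Its size rests on assumptions, and it is small if most candidates sit well above 4. This stands, which is why the mean 6 range is given.

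**Day 1 is probably outside Baseline.** SAP 3.3.2.1 read alone might suggest that the Day 1 pre-dose entry counts, which would widen the offset from criterion 8. SAP 8.2 stops before Day 1, and SAP 3.3.2.1 places its rule under the screening period. The one-day offset is the supportable reading; the looser wording still needs correcting.

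**False violators are not established.** One might infer that a subject with Baseline below 4 would be tabulated as a criterion 8 violator. SAP 5.3 refers to the screening AAPS, not Baseline, so this is possible but not shown.

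**Efficacy is exploratory.** Safety is the primary objective, there is no primary endpoint, and p-values are nominal. That lowers the stakes, but it does not recentre a shifted estimate or its confidence interval.

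**Conclusion.** The concern holds for the pooled and within-arm change from Baseline AAPS and for the absolute ≥30% responder rates. The mechanism and its direction follow from the documents. The size does not, because they give no SD or week-to-week correlation.

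Under the step 2 assumptions, part or all of a fall of about 0.2 to 0.9 points could arise with an inert drug if candidates average 4 to 5, or 0.1 to 0.4 points if they average 6. A nominally significant pooled t-test is therefore weak evidence of drug effect. The upper figures belong to the least favourable corner, with candidates averaging 4 and a weekly correlation just under 0.5.

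The window definitions also need reconciling. This affects how the pain results are read, not the primary safety objective. The change is worth making because it is cheap.

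**What to change.** 1. In criterion 8 and Protocol 5.5.1, apply the existing AAPS ≥4 requirement to one fixed diary week, for example Day -14 to Day -8, or an earlier week within the 28-day screening period.
2. In SAP 3.3.2.1 and 8.2, define Baseline AAPS identically as Day -7 to Day -1, whatever its value.
3. In Protocol 5.2, have Day 1 confirm that the qualifying week met the threshold. Re-applying the threshold to the Baseline week would bring the bias back.
4. In SAP 5.3, judge criterion 8 violations on the qualifying week only.
5. Report pooled change and responder rates with a statement that they are uncontrolled and subject to regression to the mean. For diary data already collected under the present definitions, this is the step that remains.

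**Cost.** Seven more diary days inside the existing screening period, with no extra visits or subjects; a less favourable pain reduction; and some subjects with a Baseline below 4.

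**What remains.** With adjacent weeks, the residual fall, rejection and false responder rates are those in the last column of the step 2 table. A longer gap reduces the fall further. Responder rates still cannot be attributed to the drug without a control arm.

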3.6 Exclusion Criteria

[figure not shown]
Subjects who meet any of the following criteria will be excluded from the study.

General Exclusion Criteria

[figure not shown]

Gastrointestinal Exclusion Criteria

History of >3 small bowel resections or diagnosis of short bowel 18. syndrome or who have undergone bowel resection within 6 months prior to randomization

34. Evidence of current GI infection (bacterial or parasitic) or significant infection within 45 days of Screening

4 STUDY TREATMENTS

4.1 Test Article

The Sponsor will provide adequate supplies of APD371 25 mg, 50 mg and 100 mg active drug capsules. APD371 25 mg and 100 mg strengths will have the same appearance, as will 50 mg strength If subjects in the 100 mg cohort require a 75 mg dose they will be administered one 50 mg and one 25 mg capsule, and a 50 mg dose will include dosing of one 50 mg capsule only.

4.2 Treatments Administered

APD371 drug substance (active) and bulk drug product (capsules) were manufactured under Current Good Manufacturing Practice compliance at Arena Pharmaceuticals, San Diego, CA. Bulk drug product will be packaged and labeled and shipped to participating clinical study sites prior to the study start.

4.3 Packaging, Labeling and Storage

25 mg and 100 mg APD371 capsules will be packaged 30 count in 60-cc HDPE bottles with a heat induction seal and child resistant screw cap. Each subject will be provided with 8 bottles of APD371 packaged drug product for the duration of the study, two bottles being dispensed on Day 1, Day 15, Day 29 and Day 43, respectively. If subjects in the 100 mg cohort are titrated down to a 50 mg dose they may receive additional bottles.

The 50 mg APD371 capsules will also be packaged 30 count in 60-cc HDPE bottles with heat induction seal and child resistant screw cap.

Subjects returning for assessment at the end of Wks 2, 4, 6 should take their morning APD371 medication from their newly dispensed bottles for treatment periods Wks 3-4, 5-6 and 7-8, respectively.

4.4 Test Article Accountability

The Investigator will maintain accurate records of the receipt of all study medication. In addition, accurate records will be kept regarding when and how much study medication is dispensed and used by each subject in the study. Reasons for deviation from the expected dispensing regimen must also be recorded. Study medication will be reconciled by the Sponsor monitor or contracted designee. The Investigator agrees to provide sufficient access to study medication as required for the reconciliation process to be completed in a timely fashion.

4.5 Investigational Product Retention at Study Site

At completion of the study, all study medication will be reconciled by the Sponsor's monitor and then returned at the direction of the Sponsor to be retained or destroyed according to applicable USA regulations. Prior to any action being taken with study medication after the study is completed, the Investigator will contact the Sponsor Contact listed in the Synopsis for approval of such action.

4.6 Dosage and Administration

Investigational product will be dispensed to the subjects under the supervision of the Investigator or his/her designee as determined by the randomization schedule. Dispensing will occur every two weeks at Wks 0, 2, 4 and 6.

Subjects should not crush, break, chew, or dissolve the capsules. There are no food restrictions around dosing with the exception of ingestion of grapefruit juice or prune juice.

For each of the planned dose cohorts (APD371 25 mg and 100 mg) subjects will selfadminister study treatment TID

on Days 1 to 56. Subjects will be requested not to take their morning dose of study medication on the day of a planned study visit schedule

until instructed to do so by the Investigator or his/her designee. There will be a total of 8 subjects randomized to each dose cohort.

